6.2.4 Lung Function Assessments: Lung Imaging

A LUS and EIT manual of procedures and operations will be developed for each Site. LUS and EIT imaging will be conducted at 72 hours and on Day 7 after birth (with a ± 12-hour window) at a time deemed clinically suitable by the bedside nursing and/or medical team. Where possible, both imaging modalities will be performed concurrently. If clinically appropriate to do so, EIT and LUS images will also be collected at 24 and 48 hours after birth as additional data. Data on the tolerance of lung imaging modalities will be documented. Factoring in time to allow the infant to settle between care, any position changes and image acquisition, between 30-60 minutes is anticipated to record all imaging required at each visit.

6.2.4.1 Electrical Impedance Tomography (EIT)

EIT will be used to measure regional tidal ventilation and aeration patterns using the LuMon EIT system (Sentec AG, Landquart, Switzerland), a standalone monitor. The Neonatal Research Group at the MCRI have been using the Sentec EIT system since 2014 and is familiar with all aspects of use^(22, 28-31). The Sentec EIT system integrates image reconstruction models to known characteristics of the infant chest utilising a customised electrode EIT belt system. EIT signals will be sampled at 48Hz and recorded directly into the hard drive capacity of the EIT hardware (stored as standard of care by date and time within the EIT bedside system and not identifiable patient features). A trained technician from the MCRI Neonatal Research Group will provide the necessary training and equipment (hardware and consumables) at each participating site.

The EIT system measures the regional changes in lung volumes through weak alternating currents applied to the body. These travel along the paths of least resistance through the chest, thereby creating electric potentials at the body surface. These potentials are being measured continuously by electrodes and turned into tomographic images of lung function. The electrodes are contained in a belt-like disposable textile patient interface that is fastened to the infant's thorax (**Figure 6a**).^(32, 33) The Sentec EIT electrode system includes a belt made with a knitted polyamide 6 filament yarn trilobal silver electrode fabric (approved for human use). This fabric surrounds a 0.25 cm deep and 1-2 cm wide soft medical grade padding (to ensure the belt can be applied snugly around the chest to avoid movement, and yet not interfere with normal tidal chest movement). To ensure optimal electrical conductance without the need for adhesive gel electrodes, the belts are lightly coated with standard (warmed) ultrasound gel and then wrapped around the chest at nipple level and secured with a Velcro fastener.

The EIT belt is in sterile packaging and can be left in situ for up to 72 hours and suitable for single use only. Infant handling time during belt application is <1min. PI [name] was involved in the development of this belt system,^(32, 33) and has used this EIT belt system on more than 100 infants at the Royal Children's and Royal Women's Hospitals without complication.

The Sentec EIT system (and components) are CE marked as a Class IIa medical device in the European Union and was approved by the TGA as a Class IIa device for all age groups (including neonates of all gestations) on 5 October 2022 (ARTG entry 396994). The Sentec EIT system will not be used to alter clinical care or influence clinical decision making in this study.

[figure not shown]

Figure 6a: The EIT sensor belt. Neonatal electrode belt consists of a striped electrically conductive textile, a 3D space fabric, an ultra-flexible printed circuit board and a Velcro closing system. Each of the 32 electrodes has a size of 1cm. Reproduced from Ref #(33)

The EIT belts are available in various sizes based on GA and body weight. In the case of uncertainty, the lower sized belt will be used. The belt will be coated with warmed ultrasound gel and placed around the infant's chest (at nipple level) by gently lifting the infant (or lower part) off the bed and placing the belt under the thorax or sliding the belt under the infant using the soft Velcro tag as a lead. This process takes approximately 10-20 seconds to complete and involves no greater risk than routine clinical nursing cares; if possible, it will be placed at the same time as clinical care.

An example of an EIT belt on an infant is shown in **Figure 6b**. Once in place, the wearing of the EIT belt does not interfere with any aspect of the usual clinical process. The only scenarios in which the belt may

impact usual clinical practice is when the region of the infant's chest encompassed by the belt needs to be accessed in an emergency. This includes for the provision of chest compressions and/or insertion of a chest tube or needle thoracocentesis. In both cases, the EIT belt Velcro can be undone, and the chest exposed in <2-5 seconds and would not restrict emergency therapies.

As soon as the EIT belt Velcro is secured, the EIT monitor display provides sensor quality feedback via a traffic light system display of red (bad), orange (adequate) and green (good). If the EIT belt has more than 8 of the 32 sensors indicated with red light, it will require re-adjustment or additional contact gel. If readjusting belt position does not interrupt clinical care, the team will do so. If it would interrupt clinical care, EIT recordings will not be made, and the belt removed at a time that suits the clinical team.

Once adequate/good signal contact is confirmed, EIT data will be recorded continuously (at 48 frames per second) for 2-5 minutes (if there is unacceptable signal interference or artefact, then the measurement will be repeated if practical). A total of 4 EIT images will be repeated over 2-5 minutes recording blocks. At the end of this period, the measurements will cease and the EIT belt Velcro unfastened and removed at a time that will be least invasive for the infant. EIT imaging will be performed in the supine position to a standardised gravity-dependent plane for comparisons. If the clinical team intend to re-position the infant immediately before or after an EIT recording, additional recordings in prone or lateral position will be made. If the clinical team request EIT monitoring for clinical needs, the system and belt will be kept in place until not required anymore.

Figure 6b An EIT belt in situ on an infant during resuscitative management at birth. EIT belt does not impact provision of clinical care. Reproduced with permission of parents from Ref # (22).

The following links provide a video summary of this process and how the use of EIT monitoring is quick, simple, non-invasive and does not interrupt clinical care (note: these videos are during resuscitative care at birth in a delivery room setting):

<https://doi.org/10.26188/19430372>

<https://doi.org/10.26188/14058608>

6.2.4.2 Lung Ultrasound (LUS)

LUS images will be obtained in the supine position using a GE Venue Go, Venue 50 (GE Healthcare, USA), and a Philips Affinity ultrasound system (Philips, Netherlands) with a “hockey stick,” L8-18i linear transducer set at a depth of 2.5cm and a gain of 55 decibels. The focus will be adjusted to be positioned at the pleural line. All filters will be deactivated. Video clips of 3 seconds will be acquired and stored under the allocated study identification number. If the infant is deemed unstable and not able to tolerate ultrasound imaging by the imaging team, the investigators will return at a more suitable time. The infant will be handled for <5 minutes for each LUS assessment.

6.2.4.3 Image acquisition

6 images in total will be acquired per ultrasound scan. This will comprise of the upper and lower anterior, and lower lateral regions. M-mode will be performed with each image. The ultrasound transducer will be orientated longitudinally to capture 2-3 intercostal spaces according to infant size.

6.2.4.4 Imaging procedure

If the EIT belt is in situ, it will be unfastened to allow LUS imaging without further handling. Once the infant is settled, LUS scans will be acquired. The probe will be gently placed on the infant’s chest and ultrasound gel (warmed immediately prior to scanning) will be used to ensure sufficient probe contact. Images will be acquired as per section 5. LUS image acquisition will take approximately 5 minutes.

6.2.4.5 Infant handling and safety during LUS and EIT

There will be no excessive handling associated with the ultrasounds or EIT required for this study. Infants will only be repositioned for image acquisition if it is deemed appropriate by the treating clinician and the bedside nurse midwife. If the infant is deemed clinically unstable for data acquisition, the procedure will be deferred. The site investigators will work closely with the treating clinician and bedside nurse/midwife to ensure the safe acquisition of ultrasound and images. Disruption to routine care will be minimised by coordinating data acquisition with clinical care.

6.2.4.6 Image coding

EIT Images

All EIT images will follow a standardised labelling nomenclature in the following format:

BLPRNT_[Study ID]_[Time point (DAYxx)]_[sequence order]

Time points will be recorded using the following labels:

Time Point	Label
72 Hours	DAY3
Day 7 (168 hours)	DAY7
36 Weeks PMA	36WK

Example: An infant (Study ID: 1234) receives a lung ultrasound at 72 hours (Day 3).

Therefore, the third imaging period will be labelled as: **BLPRNT_1234_DAY3_3**

LUS images

All LUS images will follow a standardised labelling nomenclature in the following format:

BLPRNT_[Study ID]_[Time point (DAYxx)]_[lung_region]

Regions must be labelled as the following:

Region	Label
Right anterior upper	RAU
Right anterior lower	RAL
Right lateral lower	RLL
Left anterior upper	LAU
Left anterior lower	LAL
Left lateral lower	LLL

Example: An infant (Study ID: 1234) receives a lung ultrasound on Day 3. The image from the right anterior upper region will be labelled as: **BLPRNT_1234_DAY3_RAU**

6.2.5 Blood Sampling and plasma isolation

Details of blood sampling and processing methodology are outlined in the BLUEPRINT Lab Processing Manual.

A minimum sample volume of 0.2ml of whole blood is required at each timepoint to perform the mass spectrometry analysis. Whole blood samples (0.5ml) will be collected into EDTA microtubes by a research or bedside nurse via either umbilical arterial line or capillary access. The required 0.2 - 0.5 ml of whole blood is consistent with the volume of blood required for common clinical investigations in preterm infants (approximately 0.3-0.5 mL for electrolyte or full blood count analysis) and represents between 0.17-0.5% of circulating blood volume (500-1500 g weight).

Blood samples will be collected at 72 hours (± 12 hours) and Day 7 (± 12 hours) post-birth from all enrolled infants. Where possible, arterial sampling will be used as this is less invasive for the infant. Capillary sampling involves breaching the skin (heel) using a micro-lancet. Micro-lancet capillary sampling is common practice in all Victorian NICUs and considered standard of care when arterial access is not available. Both arterial and capillary sampling will be conducted in accordance with current NICU blood sampling guidelines at participating sites. The ± 12 hours sampling window allows for the impact of blood sampling on the infant to be limited. Capillary blood samples will be matched to routine clinical sampling timelines to ensure there are no additional skin breaches associated with participation in the project. If routine sampling is not occurring within the allowable ± 12 -hour window, a protocol deviation will be noted in the RedCap database. All blood samples will be performed by the bedside nurse/midwife, phlebotomist or doctor who will be instructed not to persist with sampling if the procedure would expose the infant to longer distress or pain. To further ensure infant safety, a member of the study team will confirm with the clinical team the suitability of sample collection prior to each

collection based on the individual characteristics of the infant. A sample will only be taken if the treating clinician is satisfied the infant would not be harmed.

Following collection, the samples will be labelled by the bedside/research nurse in accordance with the BLUEPRINT Study Proteomics Manual of Operating Procedures and Lab Processing Manuals and forwarded to the hospital Pathology Department for processing prior to transfer to the MCRI.

Prior to mass spectrometry analysis, one plasma aliquot will be transferred to the Baker Research Institute (BRI; [name]) and immediately stored in a secure freezer at -80°C . The plasma sample barcode will be used by a MCRI research staff member to log the sample “transferred to BRI” using the secure OpenSpecimen platform. Post mass spectrometry, remnant plasma samples (including empty vials) will be transferred back to MCRI and logged as “returned to MCRI”. Mass spectrometry data files will use the de-identified barcode, with all data files uploaded to the secure server at MCRI for later analysis and incorporation in the study database. Any excess plasma will be stored at -80°C in secured and monitored freezers allocated to the Neonatal Research Group (MCRI). Any residual plasma samples will be securely stored at -80°C for a period of 10 years to facilitate potential future validation of markers identified by the Neonatal Research Group at MCRI.

6.2.6 Day 14 and Day 28 Assessment

Previous studies of LUS to predict BPD status have suggested that Day 14 and Day 28 are the most useful time points.⁽²¹⁾ LUS and EIT images will be conducted on Day 14 and Day 28 after birth (with a \pm 24-hour window) as per 72 hours and Day 7 methods (see Section 6.2.4). Suitability to obtain imaging data and best timing will be re-affirmed with the clinical team. Where feasible, the parent/legal guardian will be notified of upcoming assessments as per the manual of operating procedures. In addition, the following clinical data will be collected:

- Type of respiratory support and use of supplemental oxygen at midday on Day 14 and Day 28
- All types and duration of respiratory support used between Days 8-14 and Days 15-28
- Intubation and extubation events since Day 7
- Survival status/date of death (during hospital stay, if applicable) / reason for death
- Documentation of any adverse events and/or safety issues
- Relevant respiratory and other treatments or outcomes, including:
 - Use of postnatal steroids, including types, timing and accumulated doses
 - Use, type, delivery method and dose of exogenous surfactant
 - Use of caffeine or other respiratory stimulants
 - Use of inotropes, including types, timing and accumulated doses
 - Use of pulmonary hypertensive treatments, including types, timing and accumulated doses
 - Use of antibiotics and proven culture positive results
 - Incidences of significant brain injury (IVH, periventricular leukomalacia), pneumothorax and pulmonary interstitial emphysema, necrotising enterocolitis and retinopathy of prematurity
 - Patent ductus arteriosus (PDA) and any associated treatment
 - Incidences of other clinical events or diagnoses that may impact respiratory status
- LUS data including quality and number of images and LUS score
- EIT data including quality and number of images, belt size used and regional ventilation measures (centre of ventilation, %Tidal volume per region and inhomogeneity index)

6.2.7 36-weeks' PMA BPD Assessment

BPD status during 36 weeks' PMA will be assessed using the Modified Walsh definition and standard oxygen reduction test (ORT), and Jensen criteria for Grading from no BPD, mild, moderate and severe (Grade 0-3) (5, 10). Death before 36 weeks' PMA due to a primary respiratory cause will be coded as severe BPD using the 2018 NICHD Grade 3A BPD definition; *'early death between 14 days postnatal age and 36 weeks' PMA from persistent parenchymal lung disease and respiratory failure that is not attributable to other neonatal morbidities'*. Inclusion of death due to non-respiratory causes may result in misclassification in the prediction models. The primary and critical contributors to all deaths before 36 weeks' PMA will be documented to allow secondary analysis for 'all cause' mortality in the prediction models. The 36-week BPD Assessment should occur on the date determined to be 36+0 to 36+6 weeks PMA.

If the BPD assessment is completed outside of the 36+0 to 36+6 weeks' PMA assessment window, as the infant was discharged home from hospital early self-ventilating in air (SVIA) before 36+0 weeks PMA, then these infants will be coded as not having BPD. Should the condition of the infant change within the 36-weeks PMA (e.g. they are re-admitted to any hospital between discharge home and 36+6 weeks PMA), then the participating site must update the 36-Week PMA BPD Assessment CRF, if applicable.

Lung imaging will be repeated as per Section 6.2.4, and the appropriateness of studying the infant will be re-affirmed with the clinical staff. For scheduled weekly or pre-discharge measures, consent will also be re-affirmed with the parents/legal representative and documented in the participant's medical record as per the Manual of Operating Procedures.

6.2.8 NICU Stay

A delegated member of the study team will record data relating to the clinical course after Day 28, and then relevant secondary outcomes during NICU stay until hospital discharge, death, withdrawal, or 44 weeks' PMA (whatever comes first) for each infant; including:

- Survival status/date of death (during hospital stay, if applicable) / reason for death
- Type and duration of respiratory support and use of supplemental oxygen during stay not already documented, specifically:
 - Need for invasive respiratory support between birth and 36 weeks' PMA
 - Age at and duration of invasive respiratory support between birth and 36 weeks' PMA and discharge
 - Age at and duration of non-invasive respiratory support between birth and 36 weeks' PMA and discharge
 - Age at and duration of all modes of respiratory support between birth and 36 weeks' PMA and discharge
 - Age at and duration of supplementary oxygen between birth and 36 weeks' PMA and discharge
- Oxygen requirement at discharge
- Intubation and extubation events since Day 28
- Growth parameters
- Documentation of any adverse events and/or safety issues
- Relevant respiratory and other treatments or outcomes, including:
 - Use of postnatal steroids, including types, timing and accumulated doses
 - Use, type, delivery method and dose of exogenous surfactant
 - Use of caffeine or other respiratory stimulants

- Use of inotropes, including types, timing and accumulated doses
- Use of pulmonary hypertensive treatments, including types, timing and accumulated doses
- Use of antibiotics and proven culture positive results
- Incidences of significant brain injury (IVH, periventricular leukomalacia), pneumothorax and pulmonary interstitial emphysema, airway abnormalities or obstruction (such as sub-glottic stenosis), PDA requiring treatment, surgical procedures, necrotising enterocolitis, and retinopathy of prematurity
- Incidences of other clinical events or diagnoses that may impact respiratory status

In addition, relevant baseline maternal, antenatal, and demographic data not collected prior to Day 7 will be recorded before discharge. Consent to include families in ongoing study newsletters and other dissemination of study information will be re-affirmed during this period. Families will also be asked to confirm willingness to participate in 1- and 2-year follow-up and consent to collect contact information (phone number and email) and Medicare details. Families that agree to follow up will be provided with reminder information.

6.2.9 1Year and 2 Year corrected age Follow-Up Visit Data

A follow-up visit will occur at 1 year (12-months' corrected age \pm 1 month) and 2 years (24-months' PMA \pm 2 months) to assess for respiratory and general health outcomes. Children will be invited to attend the MCRI Research Clinic. The Research Coordinator/Study Team, or other appropriately trained staff, at the MCRI will record data relating to:

1. Mortality before 1 year and at 2 years corrected age
2. General health and well-being since last assessment, including hospital presentations and medications
3. Weight, length and head circumference
4. Respiratory events since last assessment, including hospital presentations/admissions, confirmed respiratory tract infections, wheezing episodes requiring treatment, use of steroid and/or bronchodilator treatments.
5. Smoking exposure and burden (self-reported by parent)
6. Duration of oxygen therapy after discharge (if applicable)
7. Postcode at time of assessment (smoking and postcode are needed for analysis of potential confounders, such as pollution exposure and socioeconomic class)
8. Documentation of general gross motor ability (including diagnosis of cerebral palsy) and cognitive ability, any visual impairment or blindness, any hearing impairment or deafness
9. PARCA-R Questionnaire (developmental assessment questionnaire completed by parents), if applicable

LUS and EIT imaging will be performed as per scheduled assessments during the NICU stay.

If families are unable to attend in-person for follow-up assessments, a telephone consultation questionnaire with parent/legal guardian or an online health status questionnaire (via REDCap) will be offered. In instances when a telephone consultation cannot be performed, a Direct-to-Parent Questionnaire will be forwarded to parents/legal guardians for completion (if consent provided), which

includes a brief health assessment and a validated child development assessment aimed at parents (PARCA-R Questionnaire; Dev Med Child Neurol 20 04; 46:389–97). The PARCA-R Questionnaire is a complete questionnaire that can be used to assess children’s cognitive and language development at 2 years of age.

The Direct-to-Parent questionnaire will be administered via a web-based survey located on the secure REDCap server at MCRI, in Melbourne, Australia. The child-specific link to the Direct-to-Parent questionnaire, and any alerts/reminders disseminated, will be sent electronically to parents. All communication efforts will be documented in the child’s medical record or shadow file.

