3.1.2 Secondary objectives

The secondary objectives of this study are:

1. To compare the respiratory endotypes associated with different respiratory outcomes using observational data at 72 hours after birth in preterm infants born between 22+0 and 31+6 weeks' gestation.
2. To develop the first functional classification of preterm respiratory disease using a combination of clinical, lung imaging and molecular biomarkers.

3. Determine how specific early preterm endotypes relate to a diagnosis of BPD to develop a predictive modelling tool for the early diagnosis of BPD that can be used in everyday clinical practice.
4. Determine how specific early preterm endotypes relate to outcomes of the primary NICU admission, including duration of invasive mechanical ventilation and supplementary oxygen support, mortality, need for supplementary oxygen at discharge home.
5. To characterise the respiratory health of preterm infants in the first 2 years (corrected) after birth.
6. To characterise overall childhood health of preterm infants in the first 2 years (corrected) after birth.
7. To determine the relationship between initial respiratory endotype, BPD status and early childhood respiratory health at 1 and 2 years of corrected age.
8. To determine the performance of early life endotypes against a 36-week diagnosis of BPD in predicting respiratory outcomes at 1 and 2 years of corrected age.
9. To determine the relationship between LUS-derived measures of respiratory status at 14 and 28 days after birth and BPD status.
10. To determine the relationship between EIT-derived measures of respiratory status at 14 and 28 days after birth and BPD status.
11. To use plasma proteomics to identify proteins whose expression is altered in the first 7 days of life in infants who later are diagnosed with BPD.
12. To use plasma proteomics to identify expression pathways associated with specific preterm respiratory endotypes in samples obtained at 72 hours and 7 days post-birth.
13. To determine the impact of clinical interventions on the development of the respiratory phenotype.

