Duration of invasive mechanical ventilation and supplementary oxygen support, mortality and need for supplementary oxygen at discharge home as independent outcomes and functional endotypes determined above.
To characterise the respiratory health of preterm infants in the first 2 years (corrected) after birth.
Outcome & outcome measure
Respiratory health status questionnaire, gravity-dependent and right-left lung centre of ventilation and homogeneity index (EIT*) and LUS* score (LUSS) at 1 and 2 years corrected age.
To characterise overall childhood health of preterm infants in the first 2 years (corrected) after birth.
Outcome & outcome measure
General health status defined by growth parameters and medical history since discharge and development (PARCA-R) questionnaires.
To determine the relationship between initial respiratory phenotype, BPD status and early childhood respiratory health.
Outcome & outcome measure
Respiratory phenotype at 72 hours and Day 7, BPD status and severity grade and Respiratory health outcomes at 1 and 2 years corrected age.
To determine the performance of early life endotypes against a 36-week diagnosis of BPD in predicting respiratory outcomes at 1 and 2 years of corrected age.
Outcome & outcome measure
BPD status at 36 weeks' corrected PMA using Walsh Definition and Jensen Grade of Severity, respiratory health at 1 and 2 years corrected age and functional endotypes determined above.
To determine the relationship between LUSS-derived measures* of respiratory status at 14 and 28 days after birth and BPD status.
Outcome & outcome measure

The accuracy of the blindly calculated LUS score proposed by Brat et al(27) in predicting a final diagnosis of BPD at 36 weeks (Yes/No). This score will be used as the primary lung ultrasound score incorporated into the predictive model.
To determine the relationship between EIT-derived measures of respiratory status at 14 and 28 days after birth and BPD status.

Outcome & outcome measure
 
Gravity-dependent and right-left lung centre of ventilation and homogeneity index (EIT*) at 14 and 28 days after birth.

To use plasma proteomics to identify proteins whose expression is altered in the first 7 days of life in infants who later are diagnosed with BPD.

Outcome & outcome measure
 
Difference in plasma protein abundance at 72 hours and 7 days post-birth between infants with and without BPD.

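### Recording stops at 44 weeks' PMA, but oxygen at discharge home and durations of support to discharge are outcomes, so infants still in hospital then lack the first and have the others cut short

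*Protocol*

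**What the plan says.** Section 6.2.8 (NICU Stay) sets the window for recording the clinical course after Day 28 and the secondary outcomes of the admission: "during NICU stay until hospital discharge, death, withdrawal, or 44 weeks' PMA (whatever comes first".

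The list under that sentence includes items that are complete only at discharge:

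- "Oxygen requirement at discharge"
- "Age at and duration of supplementary oxygen between birth and 36 weeks' PMA and discharge"
- "Age at and duration of invasive respiratory support between birth and 36 weeks' PMA and discharge"

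These items feed secondary objective 4 (Section 3.1.2), which relates endotypes to outcomes of the primary admission, "including duration of invasive mechanical ventilation and supplementary oxygen support, mortality, need for supplementary oxygen at discharge home". Table 3a (Section 3.2) names the outcome measures as "Duration of invasive mechanical ventilation and supplementary oxygen support, mortality and need for supplementary oxygen at discharge home as independent outcomes". Neither place mentions 44 weeks.

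Two other places describe the window without a 44-week limit. The synopsis (Exposures) has clinical data collected up to NICU discharge, and Table 5a (Section 5.2) has a column for the end of the NICU stay. The protocol gives no rule for an infant who reaches 44 weeks' PMA as an inpatient.

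**The concern.** The collection rule and the outcome definitions do not fit together. Oxygen status at discharge exists only once the infant is discharged. If recording has already ended, the value is not collected, and no analysis can supply it. Durations to discharge are observed only as far as the cut-off.

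The loss is not random. An infant reaches the cut-off only by staying in hospital a long time, and long stays go mainly with more severe illness. Missingness in the discharge oxygen outcome is therefore related to the outcome itself, and the rate among infants with a recorded value would tend to be too low. What is at stake is part of secondary objective 4. The primary objective and the BPD prediction model do not use these items.

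**Working it through.** The plan states no figure on this point, so there is none to reproduce. The check sets the passages side by side and then gives a labelled range for the size.

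**1. Which outcomes does the cut-off touch?**

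| Item | Effect if the infant is in hospital at 44 weeks' PMA |
|---|---|
| Oxygen at discharge home | Not recorded |
| Days of invasive ventilation, days of oxygen, to discharge | Observed to 44 weeks only |
| The same durations to 36 weeks' PMA | Unaffected |
| BPD status and grade (Section 6.2.7) | Unaffected |
| Death after 44 weeks | Outside this window, but mortality is an item at the 1-year and 2-year assessments (Section 6.2.9), and hospital records are checked before families are contacted (Section 7.7.3) |

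**2. Do later items fill the gap?** Section 6.2.9 asks how long oxygen was used once the child was home. A positive answer would let oxygen at discharge be inferred. It says nothing about support between 44 weeks and discharge. Follow-up is also voluntary (Section 4.2), with planned retention of just over 80% (Section 11.1). Recovery is partial.

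**3. Where does the cut-off fall?** Postnatal age at cut-off = 44 weeks minus gestation at birth.

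- Born at 22+0: 44 - 22 = 22 weeks = 154 days.
- Born at 31+6: 44 weeks - 31 weeks 6 days = 12 weeks 1 day = 85 days.

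Every infant gets the same 8 weeks after 36 weeks' PMA.

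**4. How many infants?** Inputs from Section 11.1: 550 enrolled, 5% lost before the BPD assessment, 7% overall mortality. As a check on the base, 550 × 0.95 = 522.5, against the plan's rounded 525. Survivors: 550 × 0.95 × 0.93 = 485.9, about 486.

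The share *f* of survivors still in hospital at 44 weeks is not in the protocol. Assumed values:

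| *f* | Infants without a discharge oxygen value (486 × *f*) |
|---|---|
| 1% | 5 |
| 2% | 10 |
| 5% | 24 |
| 10% | 49 |

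**5. Direction and possible size of the bias (illustration only).** Let *o* be the rate of oxygen at discharge among infants still in hospital at 44 weeks, and *r* the rate among the rest. Then true rate = *f* × *o* + (1 - *f*) × *r*. If infants without a value are dropped, observed rate = *r*. Relative understatement = 1 - *r* / true rate. Assume *o* = 60-90% and *r* = 5-15%.

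- *f* = 5%, *o* = 60%, *r* = 15%: true = 0.030 + 0.1425 = 0.1725; 1 - 0.15/0.1725 = 13%.
- *f* = 5%, *o* = 90%, *r* = 5%: true = 0.045 + 0.0475 = 0.0925; 1 - 0.05/0.0925 = 46%.

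The same formula gives 3-15% at *f* = 1% and 23-63% at *f* = 10%. The direction follows whenever *o* exceeds *r*. The size rests wholly on the three assumed inputs.

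**6. Durations.** If support continues for an assumed 2-8 weeks beyond 44 weeks, an affected infant's duration is 14-56 days too short. At *f* = 5% the cohort mean shifts by 0.05 × 14 = 0.7 to 0.05 × 56 = 2.8 days. The effect is in the upper tail.

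**The case against.** The strongest reply is that a fixed end of observation at one postmenstrual age is a legitimate choice, on the same scale as the BPD assessment. Durations can be treated as right-censored there, and the analysis plan, which is not shown, may say so. Section 6.2.8 itself lists oxygen at discharge, and the synopsis and Table 5a run to the end of the NICU stay. The 44-week clause may therefore be a slip of wording and not an intended loss of data.

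For the durations this largely stands. It does not answer the discharge oxygen item, where the loss occurs at collection, and a slip still needs correcting because sites will follow the sentence as it reads.

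A reader might also infer four stronger claims. The documents do not support them.

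- **The cut-off removes exactly the infants with the worst lung disease.** Surgery, necrotising enterocolitis and brain injury, all on the Section 6.2.8 list, can also prolong a stay. The most that can be said is mainly the more severely ill.
- **Mortality is lost too.** The follow-up mortality item and the hospital-record check should find most late deaths without the family having to attend.
- **The most severe infants contribute the least information, so endotype associations are weakened.** An infant on support at 44 weeks has 85 to 154 days of observed support, the longest recordable for its gestation, and keeps all its data to 36 weeks' PMA. No effect on the associations has been shown.
- **A definite share of oxygen-at-discharge events is lost.** Any such percentage needs the number of inpatients at 44 weeks and two oxygen rates, none of which the protocol gives.

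**Conclusion.** The point holds in a narrow form. Section 6.2.8 conflicts with objective 4, Table 3a, the synopsis, Table 5a and its own item list. Followed literally, infants still in hospital at 44 weeks' PMA have no oxygen status at discharge, and their to-discharge durations are cut. The missingness is related to the outcome and would tend to understate oxygen at discharge.

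The number affected is about 5 to 49 infants, assuming that 1-10% of some 486 survivors are still inpatients. The text conflict is certain, while the number and the bias are assumption-based. It concerns part of one of 13 secondary objectives, and is worth correcting because the correction is cheap.

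**What to change.** Preferred: for four items only (date of discharge, oxygen at discharge home, total days of invasive ventilation, total days of oxygen), continue chart review to first discharge home or death, with no 44-week cut. The other items in Section 6.2.8 can keep the present window. The cost is one case report form rule and extra chart review for a few long-stay infants. Infants who have already passed 44 weeks would need their values retrieved from the records.

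Alternative, if the cut-off is to stay: redefine the outcome as oxygen status at discharge or 44 weeks' PMA, whichever is first, record that status at 44 weeks for infants still in hospital, and treat durations as right-censored there. This costs no further collection after 44 weeks, but the outcome is then no longer oxygen at discharge home.

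Either way, the synopsis, Section 3.1.2, Table 3a, Table 5a and Section 6.2.8 should state the same window and the same endpoint.
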